### Statistical Analysis

Descriptive statistics for qualitative variables in the study are presented as counts and percentages, while descriptive statistics for quantitative variables include mean, standard deviation, median, minimum, and maximum values. For comparisons based on the occurrence rates of relevant variables among groups, Pearson chi-square or Fisher Freeman Halton tests will be employed. In the detailed comparison of groups with observed differences, the Bonferroni correction will be applied. The normal distribution conformity of quantitative variables will be assessed using the Kolmogorov-Smirnov test. One-way analysis of variance (ANOVA) will be utilized for the comparison of means among more than two groups, with the Tukey test employed as a post hoc test for multiple comparisons. Kruskall-Wallis test will be applied for the median comparison of more than two independent groups, and Dunn test will be used for pairwise comparisons. For repeated measurements of variables showing normal distribution changes between periods, analysis of variance will be applied, while the Friedman test will be used for variables not showing normal distribution. Additionally, two-way analysis of variance will be used to

examine changes between groups and periods. The statistical significance level will be set at 0.05, and the SPSS (version 26) package program will be used for calculations. Consent to conduct the study was obtained from Local Ethic Committee of Bezmialem Vakif University.

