## Study Protocol

In this study, the combination of Pericapsular Nerve Group (PENG) block and low-dose intrathecal morphine with spinal anesthesia in hip arthroplasty is aimed to be compared with PENG alone and intrathecal morphine alone in terms of morphine consumption, postoperative pain, and recovery quality scores during the postoperative 48-hour period.

After approval from the Ethics Committee of Bezmialem Vakif University Medical Faculty, the study will be conducted on 90 adult patients aged 18-90 years, classified as ASA I-IV, who will undergo hip surgery. This prospective, randomized, and double-blind clinical trial has been planned. Randomization will be achieved by assigning patients to study groups entirely by chance, and selection bias will be prevented. For this purpose, MedCalc version 16 statistical software for Windows ([medcalc.com.tr](http://medcalc.com.tr)) will be used. Patients will be divided into three groups: Pericapsular nerve group block plus spinal anesthesia with bupivacaine (Group P: n=30), Spinal anesthesia with bupivacaine and morphine (Group M: n=30), and pericapsular nerve group block plus spinal anesthesia with bupivacaine and morphine (Group P+M: n=30). After the patients are taken to the operating room, standard monitoring with non-invasive blood pressure (NIBP), heart rate (HR), peripheral oxygen saturation (SpO2), and electrocardiography (EKG) will be conducted. All patients will receive 2-6 L/min of oxygen through a nasal cannula. Preoperative visual analog scale (VAS) for pain and Quality of Recovery (QoR-15) values will be recorded for all patients. As premedication, all patients will receive 0.03 mg/kg midazolam.

In this prospective, double-blind, randomized clinical trial, researchers will be unaware of which treatment will be applied to patients in the study groups and which of these treatments is beneficial or not. Patients will also be unaware of which treatment is administered to them.

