### Groups:

**Group P:** Patients in this group will undergo ultrasound-guided block using a linear or convex ultrasound probe in the supine position before spinal anesthesia. The block procedure will involve the use of a local anesthetic solution (10-20 ml of 0.25% bupivacaine, 2 mg dexamethasone, and 5 mcg.ml-1 epinephrine) and a Stimuplex Ultra 360 22G 80 mm block needle (B. Braun Medical AG, Melsungen, Germany). Subsequently, spinal anesthesia will be administered at the L3-L4 intervertebral level with 10-15 mg of heavy bupivacaine while the patient is in a sitting position.

**Group M:** Patients will receive subarachnoid block without Pericapsular Nerve Group block. Subarachnoid block will be administered at the L3-L4 intervertebral level by adding 10-15 mg bupivacaine with 100 µg of morphine.

**Group P+M:** Patients will undergo ultrasound-guided block using a linear or convex ultrasound probe in the supine position before spinal anesthesia. The block procedure will involve the use of a local anesthetic solution (10-20 ml of 0.25% bupivacaine, 2 mg dexamethasone, and 5 mcg.ml-1 epinephrine)

and a Stimuplex Ultra 360 22G 80 mm block needle (B. Braun Medical AG, Melsungen, Germany). Subarachnoid block will be administered at the L3-L4 intervertebral level by adding 10-15 mg bupivacaine with 100 µg of morphine.

Sensory block control at T8-T10 level will be assessed in all three groups. Visual analog scale (VAS) for pain and 15-degree leg elevation will be measured in all groups 10 minutes after the completion of the block. Postoperative nausea and vomiting will be monitored and recorded. The same anesthesiologist will administer both the block and spinal anesthesia to all patients.

After the block, all patients will be continuously monitored for signs of local anesthetic toxicity every 5 minutes with non-invasive blood pressure, continuous EKG, and pulse oximetry, for 30 minutes. During the perioperative period, VAS (at 1st, 6th, 12th, 24th, and 48th hours), QoR-15 score values, and rescue analgesic requirements of patients will be recorded.

Intravenous Patient-Controlled Analgesia (IV PCA) device will be installed, and patients who are hemodynamically and respiratory stable in the recovery unit will be transferred to the ward.

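### Nausea and vomiting would be judged by a three-arm test and Bonferroni-corrected pairs with no risk difference or interval, so a non-significant result would put no bound on the excess still possible with intrathecal morphine

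*Combined protocol and SAP*

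**What the plan says.** The Groups section states: "Postoperative nausea and vomiting will be monitored and recorded". No other postoperative adverse effect is named as recorded. Local anesthetic toxicity is watched for during the 30 minutes after the block ("all patients will be continuously monitored for signs of local anesthetic toxicity every 5 minutes"), but it is not named as an outcome.

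The Statistical Analysis section has one route for a yes/no outcome: "For comparisons based on the occurrence rates of relevant variables among groups, Pearson chi-square or Fisher Freeman Halton tests will be employed". The follow-up is: "In the detailed comparison of groups with observed differences, the Bonferroni correction will be applied". The level is general: "The statistical significance level will be set at 0.05". The descriptive plan is: "Descriptive statistics for qualitative variables in the study are presented as counts and percentages". No risk difference, risk ratio or confidence interval is planned for any binary outcome, and no morphine v no-morphine contrast is specified.

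The Statistical Analysis section does not name nausea and vomiting. That this rule applies to it is an inference, but no other rule for a binary outcome is given.

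**The concern.** Testing the three arms together and then correcting the pairs limits false claims of a difference. For a benefit that is the cautious direction. For a harm, the costlier error is often the missed excess, and a stricter threshold makes that error more likely.

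The pair that isolates intrathecal morphine is P+M v P. Both arms get the same block solution and the same range of spinal bupivacaine, and only P+M gets the 100 µg of intrathecal morphine. The plan would deliver a corrected test for this pair and no estimate. If the test is not significant, the report holds a P value and three percentages. It does not say whether a large excess has been ruled out or merely not detected. A judgement on whether the combination is worthwhile needs that distinction.

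**Working it through.** **Inputs from the documents.** "the study will be conducted on 90 adult patients aged 18-90 years", in three arms of 30. Significance level 0.05, taken as two-sided because the sidedness is not stated. Three possible pairs, so Bonferroni gives 0.05/3 = 0.0167 per pair; the divisor of three is an assumption.

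**Inputs assumed.** The documents give no nausea and vomiting rates, target difference or power, so there is no planned figure to reproduce. Four scenarios are used, each with the same rate in both morphine arms.

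**Method.** Exact enumeration of all three-arm binomial outcomes with 30 per arm. Planned route: Pearson chi-square on 2 df at 0.05, then Pearson pairs at 0.0167, counted only in the direction of harm. Comparator: the unadjusted 95% Newcombe (score) interval for P+M minus P lies wholly above zero.

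| True rate, P v both morphine arms | Overall test significant | Plan flags at least one morphine arm as worse than P | Plan flags P+M as worse than P | Same pair, Bonferroni without the overall test | Same pair, unadjusted 95% interval |
|---|---|---|---|---|---|
| 20% v 40% | 39% | 36% | 23.8% | 24.0% | 39.2% |
| 20% v 45% | 56% | 53% | 37.3% | 37.6% | 54.5% |
| 20% v 50% | 72% | 68% | 52.4% | 52.5% | 69.2% |
| 30% v 50% | 35% | 30% | 19.4% | 19.5% | 35.1% |

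**Where the loss comes from.**
- Whole planned route against the unadjusted interval, P+M v P: 39.2 − 23.8 = 15.4; 54.5 − 37.3 = 17.2; 69.2 − 52.4 = 16.8; 35.1 − 19.4 = 15.7 percentage points.
- The part due to the overall test once Bonferroni applies: 24.0 − 23.8 = 0.2; 37.6 − 37.3 = 0.3; 52.5 − 52.4 = 0.1; 19.5 − 19.4 = 0.1. So nearly all of the loss on this pair is the Bonferroni level.
- Arm size matters more. Even unadjusted, the pair is detected in only 39% and 35% of trials at a 20-point excess.

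**Wider range.** With Group P at 10% to 40%, the plan flags at least one morphine arm in 29% to 46% of trials at a 20-point excess, 63% to 80% at 30 points and 89% to 96% at 40 points. It passes 50% at an excess of about 22 to 27 points.

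**Precision.** The simple half-width for one pair at 20% v 40% is 1.96 × √(0.2×0.8/30 + 0.4×0.6/30) = 1.96 × √0.01333 = 0.226. The mean Newcombe half-width is 21.6 to 22.7 points across the scenarios. Among trials in which the plan does not flag P+M v P, at least 96% have an upper limit of 20 points or more in all four scenarios.

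**Worked case.** Suppose 6/30 in P and 12/30 in each morphine arm.
- Overall test: the pooled rate is 30/90 = 0.333, so chi-square = 30 × [(0.2 − 0.333)² + 2 × (0.4 − 0.333)²] / (0.333 × 0.667) = 3.6. The 5% critical value on 2 df is 5.99, so the result is not significant.
- Wilson limits: 0.095 to 0.373 for 6/30, and 0.246 to 0.577 for 12/30.
- Newcombe lower limit: 0.20 − √[(0.400 − 0.246)² + (0.373 − 0.200)²] = −0.03.
- Newcombe upper limit: 0.20 + √[(0.577 − 0.400)² + (0.200 − 0.095)²] = 0.41.

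The planned report would show a non-significant result. The data would be compatible with anything from 3 points fewer to 41 points more patients affected.

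**The case against.** **A stronger reading.** A reader might infer that any real excess with intrathecal morphine would usually be reported as no difference. The documents do not support that, because they give no rates and the answer depends on the size of the excess. At 20% v 45% or 50% the plan flags some morphine arm more often than not, and at 30 points or more it does so in 63% to 96% of trials. Two arms receive intrathecal morphine, so scoring only P+M v P overstates the loss. On flagging any morphine arm, the plan (36%, 53%, 68%, 30%) is only about 1 to 5 points below the single unadjusted interval. All of this stands.

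**Both steps to blame?** A reader might also hold the overall test and the correction equally responsible. The table shows otherwise: with Bonferroni in place, the overall test costs at most 0.3 points.

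**Sample size is the real problem.** This stands as the main cause, and an interval does not make 30 per arm larger. Low precision is, however, a reason to show the interval.

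**Readers can work it out.** Counts and percentages are planned, so a careful reader could derive the interval. True, but that leaves the authors' own report without it.

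**Nothing says non-significance will be called absence of harm.** Correct; the plan does not say so. Nor does it prevent it.

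**Nausea and vomiting is not part of the stated aim.** Correct. The Study Protocol names morphine consumption, pain and recovery quality. This limits the weight of the point but does not remove it, because the outcome is collected and will be compared.

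**Conclusion.** The concern holds in a limited form. The only analysis route for nausea and vomiting gives tests and no estimate of the difference between arms. For a true excess of about 20 points, the plan would more often than not flag neither morphine arm (flagged in 29% to 46% of trials for Group P rates of 10% to 40%). In the four scenarios, failing to flag P+M v P leaves an excess of 20 points or more compatible with the data at least 96% of the time, and the report would not show it. The main cause is 30 patients per arm. The Bonferroni level takes a further 15 to 17 points from the P+M v P pair.

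These figures rest on assumed rates, equal rates in the two morphine arms, Pearson tests, three pairs in the correction, and the inference that the general rule covers nausea and vomiting. The absence of a planned risk difference or interval rests on none of these assumptions except the last.

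**What to change.** In the Statistical Analysis section, name nausea and vomiting and state that, whatever the overall test shows, the report will give:

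- the number and percentage of patients affected in each arm, with a statement of what counts as affected and over what period, since neither is defined;
- risk differences with unadjusted 95% Newcombe (score) intervals for P+M minus P (intrathecal morphine with the block held constant), P+M minus M (the block with intrathecal morphine held constant), and M minus P, noting that M and P also differ by the block;
- as a supportive contrast, pooled intrathecal morphine (60) minus none (30). In the four scenarios this is significant at 0.05 in 48%, 67%, 82% and 44% of trials. At 20% v 40% its simple half-width is 1.96 × √(0.2×0.8/30 + 0.4×0.6/60) = 0.189, against 0.226 for one pair. It carries the same caveat about the block.

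Add that a non-significant result will not be described as absence of harm. Bonferroni can stay for the other occurrence rates.

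The cost is a few lines of text and analysis on data already collected, with no extra patients or visits. The downside is a few more chance flags: with equal 30% rates, a false excess for P+M over P appears about 2.4% of the time instead of 0.8%. The intervals remain wide, because the change reports the imprecision and does not reduce it. No dose or clinical rule is affected.

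### Preoperative VAS and QoR-15 are collected, but no between-group analysis adjusts for them, and their place in the two-way ANOVA is not stated

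*Combined protocol and SAP*

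**What the plan says.** The Study Protocol section names postoperative pain and recovery quality among the outcomes to be compared, and provides a baseline for both: "Preoperative visual analog scale (VAS) for pain and Quality of Recovery (QoR-15) values will be recorded for all patients". Under Groups, a further VAS is "measured in all groups 10 minutes after the completion of the block", and the follow-up reads "VAS (at 1st, 6th, 12th, 24th, and 48th hours), QoR-15 score values, and rescue analgesic requirements of patients will be recorded". The hours are attached to VAS; no separate times are clearly given for QoR-15.

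The Statistical Analysis section sets out the between-group tests. For means: "One-way analysis of variance (ANOVA) will be utilized for the comparison of means among more than two groups". Pairs of groups are then compared by Tukey's method. The alternative is the Kruskal-Wallis "test will be applied for the median comparison of more than two independent groups, and Dunn test will be used for pairwise comparisons". Changes over time are tested by a repeated-measures ANOVA or the Friedman test. A two-way ANOVA is then meant to "examine changes between groups and periods".

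Nowhere is there a covariate, an ANCOVA, a change-from-baseline endpoint or a list of the time points that count as periods.

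**The concern.** A preoperative score of the same kind as the outcome is usually a good candidate covariate. Here it is collected on everyone, and no between-group test is said to use it. The only model that could bring it in is the two-way ANOVA, and that can be read two ways.

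- **The preoperative value is not a period.** Baseline then plays no part in comparing the groups.
- **The preoperative value is a period.** The group-by-period contrast then behaves like a change score, which is less efficient than ANCOVA and can be less precise than no adjustment at all. The group main effect is also diluted, because it averages in a time point at which no treatment effect can exist.

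The stakes are a wider confidence interval than the data allow, an estimate that carries part of any chance baseline gap, and a decision about baseline that could be made after the results are seen.

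**Working it through.** The plan states no power, effect size, SD or dropout, so there is no figure of its own to reproduce. The calculation below only sizes the issue.

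**Inputs from the documents:** 3 groups, 30 per group (90 in total), significance level 0.05, Tukey test for pairs.

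**Assumptions, not in the documents:** two-sided testing; normal data; a true difference of 0.6 SD for one pair; one postoperative time point; rho from 0 to 0.6.

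**1. Unadjusted comparison.** The Tukey critical value on the t scale is q(0.95; 3, 87)/√2 = 2.384. The standard error of a pairwise difference is √(2/30) = 0.258 SD. The noncentrality is 0.6/0.258 = 2.32, and power from the noncentral t is 0.479. The difference detectable with 80% power is 0.835 SD.

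**2. ANCOVA.** Residual variance is (1 − rho²)(1 + 1/85), where 1/85 (about 1.2%) is the price of estimating one slope. With 86 degrees of freedom the critical value is 2.385. The equivalent n per group, before that price, is 30/(1 − rho²).

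| rho | Equivalent n per group | Power at 0.6 SD | Difference for 80% power (SD) |
|---|---|---|---|
| unadjusted | 30 | 0.479 | 0.835 |
| 0 | 30.0 | 0.473 | 0.840 |
| 0.2 | 31.3 | 0.492 | 0.823 |
| 0.3 | 33.0 | 0.517 | 0.801 |
| 0.5 | 40.0 | 0.612 | 0.727 |
| 0.6 | 46.9 | 0.692 | 0.672 |

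A simulation of 40,000 trials per rho agreed (unadjusted power 0.476–0.483; ANCOVA 0.471 at rho 0 to 0.690 at rho 0.6). Familywise error was 4.8–5.2% for both methods.

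**3. Preoperative value treated as a period.** Take the simplest case, one preoperative and one postoperative value with equal SDs. The contrast has variance 2(1 − rho). At rho 0.3 this is 1.40, against 0.91 for ANCOVA before the slope cost and 1 unadjusted. That is worth 30/1.40 = 21.4 patients per group, with power 0.342. It matches the unadjusted analysis at rho 0.5, where 2(1 − 0.5) = 1, and is worse below that. As for the group main effect, a constant postoperative difference shrinks to 5/6 of its size with one preoperative and five postoperative VAS times, and to 1/2 with one preoperative and one postoperative QoR-15.

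**4. Chance baseline gaps.** For a given pair, P(gap > 0.5 SD) = 2·P(Z > 0.5/0.258) = 0.053. For at least one of the three pairs, from the distribution of the range of three means, it is 0.128. The unadjusted difference shifts by rho × gap: 0.3 × 0.5 = 0.15 SD, up to 0.6 × 0.5 = 0.30 SD. This is another view of the variance that ANCOVA removes in step 2, not an additional loss.

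**The case against.** The best counter-argument is that this is a matter of efficiency and not an error. One-way ANOVA with Tukey, or Kruskal-Wallis with Dunn, is a legitimate analysis of a randomized trial, and its error rate is held. That stands, and it limits how serious the point can be.

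The size of the gain rests on assumptions. Neither rho nor the 0.6 SD difference is in the documents, and at rho 0.3 power rises only from 48% to 52%. All patients have scheduled paracetamol and morphine PCA, and tramadol is tied to the pain score, so postoperative VAS may be compressed and only weakly related to preoperative pain. That is plausible, and it is why no single rho is relied on here.

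Three further limits also stand. The 34% power figure illustrates a single pre/post contrast; it is not the power of a test the plan names, and a group-by-period test over five VAS times was not computed. Nothing was quantified for the rank tests. And because no adjusted model is listed, adding one later would be a visible departure, so the latitude hidden in the current text is mainly which time points count as periods.

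None of this supplies the missing specification. One could say that the two-way ANOVA already deals with baseline, but the plan does not say so and names no interaction test.

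**Conclusion.** The concern holds. The plan collects preoperative VAS and QoR-15, specifies no between-group analysis that adjusts for them, and does not say whether they enter the two-way ANOVA.

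This is a loss of precision and a gap in pre-specification, not overall bias or type I error inflation. Under the stated assumptions the gain from adjustment runs from nothing (power 48% against 47% at rho 0) through small (52% at rho 0.3) to substantial (61% at 0.5, 69% at 0.6). The reason to act does not depend on a high rho: the downside is about half a percentage point of power, and the role of baseline needs to be fixed in advance in any case. The point applies to VAS and QoR-15 only. The change should be made, but the planned tests are not invalid without it. Confidence in the size is moderate, because rho is unknown.

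**What to change.** In the Statistical Analysis section:

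- Name as the main between-group analysis of postoperative VAS and QoR-15 an ANCOVA, or a longitudinal model across the postoperative times, with group and the matching preoperative value as covariate.
- List the period levels of the two-way analysis and state that the preoperative value is a covariate and not a period. Give the QoR-15 assessment times, which a longitudinal model needs.
- State that the VAS taken 10 minutes after the block is not used as a covariate, because it is measured after treatment has begun.
- Report adjusted mean differences for the three pairs with Tukey-type 95% confidence intervals.
- Keep ANOVA/Tukey and Kruskal-Wallis/Dunn as supportive analyses. For skewed scores, pre-specify robust or bootstrap standard errors or a rank-based ANCOVA.

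The cost is wording and one degree of freedom, about 1.2% of variance if rho is 0. The preoperative values are already planned for collection.

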During the postoperative period, all patients will receive 1 g of intravenous paracetamol every 8 hours. Morphine PCA (concentration: 0.1mg/ml, bolus dose: 1 mg, lockout time: 10 minutes, basal infusion rate: 0 mg) will be adjusted, and intravenous Patient-Controlled Analgesia (PCA) will be applied.

Rescue analgesia will be provided with 50 mg tramadol upon request or when  $VAS \geq 4$  and will be recorded.

Patients experiencing nausea or vomiting at any time will receive ondansetron intravenously at a dose of 0.15 mg/kg, and this dose will be repeated if necessary.

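### The 48-hour morphine comparison names no baseline covariate; prespecifying age and ASA class (optionally preoperative VAS) could gain modest precision at low cost

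*Combined protocol and SAP*

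**What the plan says.** The aim in the Study Protocol section compares the three groups "in terms of morphine consumption, postoperative pain, and recovery quality scores during the postoperative 48-hour period". Morphine use comes first in that list but is not labelled primary. It arises after surgery: "intravenous Patient-Controlled Analgesia (PCA) will be applied" (Groups section), so no preoperative value can exist.

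The trial enrols "90 adult patients aged 18-90 years, classified as ASA I-IV", 30 per group. On allocation it says "Randomization will be achieved by assigning patients to study groups entirely by chance", and no stratification by age or ASA is mentioned. It also says "Preoperative visual analog scale (VAS) for pain and Quality of Recovery (QoR-15) values will be recorded for all patients".

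For group comparisons of quantitative variables, the Statistical Analysis section says "One-way analysis of variance (ANOVA) will be utilized for the comparison of means among more than two groups", followed by Tukey, or else Kruskal-Wallis followed by Dunn. It adds repeated-measures ANOVA or Friedman for change over time, and a two-way ANOVA whose factors are group and period. No analysis of covariance, regression or baseline covariate is named.

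**The concern.** Age and ASA class describe eligibility, so they are in hand for every patient before treatment. An age span of 72 years (90 − 18) and four ASA classes leave room for wide variation in postoperative opioid use. If these variables do predict morphine use, a one-way test leaves that variation in the error term and the intervals for P+M v P and P+M v M are wider than they need be. Adjusting VAS or QoR-15 for its own baseline would not help the morphine outcome, so the matter needs its own sentence. Without one, any later adjustment for age or ASA would be a post hoc choice open to challenge.

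**Working it through.** **The plan's own figure.** The only design figure is 90 patients, 30 per group. No power, effect size, SD or dropout rate is given, so it cannot be reproduced. As a benchmark, the pairwise difference with 80% power at 30 per arm is

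- unadjusted for multiplicity, two-sided 0.05: (1.960 + 0.842) × √(2/30) = 0.723 SD;
- at the Tukey critical value of 2.384 (three groups, 87 df): (2.384 + 0.842) × √(2/30) = 0.833 SD.

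**Inputs for the comparison.**

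- From the documents: N = 90, k = 3 groups, 30 per arm, significance level 0.05, Tukey for pairwise comparisons.
- Assumed: a true pairwise difference of 0.7 SD, and a multiple correlation R of the covariates with 48-hour morphine use from 0 to 0.5.
- The model adjusted for has p = 2 covariate terms: age as a continuous term, and one ASA term.

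**Formulas.**

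- Expected penalty for chance covariate imbalance: 1 + p/(N − k − p − 1) = 1 + 2/84 = 1.0238.
- Variance factor: v = (1 − R²) × 1.0238.
- Equivalent patients per arm: 30/v.
- Power: non-central t with ncp = 0.7/√(2/30)/√v. Error df are 87 unadjusted and 85 adjusted; Tukey critical values are 2.384 and 2.385.

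Unadjusted: ncp = 0.7/0.2582 = 2.711, power 62.9%.

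| R | R² | v | Equivalent n per arm | Power | Change, points |
|---|---|---|---|---|---|
| 0 | 0 | 1.024 | 29.3 | 61.6% | −1.3 |
| 0.1 | 0.01 | 1.014 | 29.6 | 62.1% | −0.8 |
| 0.2 | 0.04 | 0.983 | 30.5 | 63.7% | +0.8 |
| 0.3 | 0.09 | 0.932 | 32.2 | 66.4% | +3.5 |
| 0.4 | 0.16 | 0.860 | 34.9 | 70.4% | +7.5 |
| 0.5 | 0.25 | 0.768 | 39.1 | 75.9% | +13.0 |

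(Changes are differences of the rounded powers; at R = 0 the unrounded loss is 1.2 points.)

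**Break-even.** v = 1 when R² = 1 − 1/1.0238 = 2/86 = 2.3%, that is R of about 0.15.

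**Adding preoperative VAS as a third term.** The penalty becomes 1 + 3/83 = 1.036 and break-even R² becomes 3/86 = 3.5%. With 84 df, power at R = 0 is 61.0%, a loss of 1.9 points.

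**The case against.** **The gain is not shown by the documents.** A reader might infer that precision is certainly given up, and that recovering it is free. Neither follows. No section links age, ASA or preoperative VAS to morphine use, and below R of about 0.15 adjustment slightly loses power. This objection stands, which is why the range above starts at zero.

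**The unadjusted analysis is not faulty.** A reader might also infer that uneven case mix biases the morphine contrast, since nothing in the allocation balances age or ASA. Under randomisation the contrast is unbiased, and chance imbalance is already in its standard error. Two arms of 30 differ by more than 0.4 SD in mean age in about 12% of trials (0.4/0.2582 = 1.55, two-sided normal tail). With a correlation of 0.4 that moves the contrast by 0.4 × 0.4 = 0.16 SD, against a standard error of 0.258 SD. This is the same noise that adjustment reduces, not a second harm. The objection stands in full.

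**The ANOVA sentence is generic.** It does not name morphine, and a non-normal outcome would go to Kruskal-Wallis. That is true, and the power figures apply only to the normal-theory route. The rank route has no covariate either, so the gap is the same on both.

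**Choice of covariates.** Preoperative VAS and QoR-15 are also recorded for all patients and could serve as covariates for morphine. That stands, and it widens the fix without undermining it. The figures depend on the covariates' joint R and do not show what ASA adds beyond age.

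**Conclusion.** The point holds as a modest, low-cost improvement in precision, not as an error of validity. The plan tests 48-hour morphine use without a covariate on either route, although usable entry variables are held for all 90 patients. For a 0.7 SD difference, power moves from 62.9% to between 61.6% and 75.9% as R runs from 0 to 0.5. The likely downside is about one power point; the upside is 3.5 points at R = 0.3 and 7.5 at R = 0.4.

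These sizes rest on an assumed effect, an assumed range for R, two covariate terms, approximate normality and complete data on 30 per arm. The absence of covariates does not rest on any assumption; the benefit of adding them does.

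**What to change.** Add to the Statistical Analysis section, in words such as these: 48-hour morphine consumption will be compared by a linear model with terms for group, age (continuous) and ASA class (one term, its coding stated in advance); the contrasts reported are P+M v P and P+M v M, with the plan's multiplicity control kept. Preoperative VAS may be added as a further term. If a rank analysis is used, apply rank analysis of covariance with the same covariates.

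Name the covariates before unblinding and do not select them by tests of baseline differences. Use only the preoperative VAS: the reading taken 10 minutes after the block follows treatment and should not be a covariate.

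The cost is a sentence and one extra model, with no new patients or data and no change to patient care. The downsides are a loss of about one power point if age and ASA are not prognostic (about two with preoperative VAS as a third term), and the assumption that the age effect is roughly linear.

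### The aim names two comparisons with the combination arm, but Tukey corrects for three; a two-contrast stepwise test would give modestly more power at no cost in patients

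*Combined protocol and SAP*

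**What the plan says.** The Study Protocol section describes three arms of 30: P (PENG block), M (intrathecal morphine) and P+M (both). It states that the combination "is aimed to be compared with PENG alone and intrathecal morphine alone". The outcomes it lists are morphine use, pain and quality of recovery over 48 hours after surgery. That is two comparisons sharing one arm. P v M is not among them.

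The Statistical Analysis section names no planned contrasts. It prescribes a three-group test followed by a post hoc procedure that depends on the type of outcome:

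- **Means:** one-way ANOVA, "with the Tukey test employed as a post hoc test for multiple comparisons".
- **Ranks:** Kruskal-Wallis, after which "Dunn test will be used for pairwise comparisons". No adjustment and no number of pairs is given.
- **Rates:** chi-square or Fisher-Freeman-Halton, then: "In the detailed comparison of groups with observed differences, the Bonferroni correction will be applied". The divisor is not given.

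On the error rate it says only: "The statistical significance level will be set at 0.05".

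**The concern.** The question is many-to-one (the combination against each component), while the method for means is all-pairs. Tukey's critical value protects three differences, so part of the error allowance goes to a pair the aim does not ask about. With 30 per arm there is little power to spare, and the documents give no planned power that could absorb the loss. At stake are wider intervals and a lower chance of detecting a real benefit of the combination over each component. The Dunn and Bonferroni wording raises a related issue: the size of the family is left open and could be settled after the data are seen.

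**Working it through.** **Inputs from the documents.** Three arms of 30, 90 in total (Study Protocol); significance level 0.05 (Statistical Analysis). 3 × 30 = 90 agrees, but the 90 cannot be derived, because no effect size, SD, target power or dropout rate is given.

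**Assumptions.** Two-sided tests, normal outcomes, a common SD, and true differences d in SD units. Each calculation concerns one outcome.

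**Step 1: critical values.** Degrees of freedom are 90 − 3 = 87.

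- Tukey, three pairs: q(0.95; 3, 87)/√2 = 2.384 (per-comparison alpha 0.0193).
- Dunnett, two contrasts: the c for which both |t| stay below c with probability 0.95, correlation 0.5 from the shared arm: 2.249 (0.0271).
- Bonferroni over two: 2.281 (0.0250). Over three: 2.441 (0.0167).
- Unadjusted: 1.988 (0.0500).

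**Step 2: interval width.** The standard error of a difference is √(2/30) = 0.258 SD. Half-widths are 2.384 × 0.258 = 0.616 SD (Tukey) and 2.249 × 0.258 = 0.581 SD (single-step Dunnett). The squared ratio is about 1.12. For 80% power on one contrast, the ratio of sample sizes is ((2.384 + 0.842)/(2.249 + 0.842))² = 1.09.

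**Step 3: cost of the third pair, like for like.** Both procedures are single-step; power comes from the noncentral t with noncentrality d/√(2/30).

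| d (assumed) | Tukey | Dunnett, single-step | Gain (points) |
|---|---|---|---|
| 0.5 | 33.2% | 38.2% | 5.0 |
| 0.6 | 47.9% | 53.2% | 5.3 |
| 0.7 | 62.9% | 67.8% | 4.9 |
| 0.8 | 76.1% | 80.1% | 4.0 |
| 1.0 | 92.9% | 94.6% | 1.7 |

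The largest gap is 5.3 points, near d = 0.61. The difference detectable with 80% power is 0.835 SD with Tukey and 0.799 SD with Dunnett.

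**Step 4: adding step-down testing.** The larger |t| is compared with 2.249; if it passes, the other is compared with 1.988. The last two columns are simulated. The closed all-pairs test requires the ANOVA F at 0.05 and then tests each pair at 0.05, so it keeps P v M. Power for P+M v M:

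| True difference v M / v P (assumed) | Tukey | Single-step Dunnett | Step-down Dunnett | Closed all-pairs |
|---|---|---|---|---|
| 0.6 / 0.6 SD | 47.9% | 53.2% | 58.0% | 56.1% |
| 0.7 / 1.0 SD | 62.9% | 67.8% | 75.9% | 75.9% |
| 0.8 / 0.8 SD | 76.1% | 80.1% | 84.3% | 83.4% |
| 0.7 / 0 SD | 62.9% | 67.8% | 68.0% | 71.2% |

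The step-down gain over Tukey is 10.1, 13.0, 8.2 and 5.1 points. In the 0.7/1.0 case, 67.8 − 62.9 = 4.9 points come from dropping the third pair and 75.9 − 67.8 = 8.1 from testing stepwise.

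A contrast with a true difference of 1.0 SD has less room. Even an unadjusted test reaches only 96.9%, so its gain cannot exceed 96.9 − 92.9 = 4.0 points.

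Power to show both contrasts rises, from Tukey to step-down Dunnett, from 61.3% to 75.3% (0.7/1.0), from 31.6% to 46.6% (0.6/0.6) and from 63.6% to 77.4% (0.8/0.8).

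**Step 5: error control.** The simulated family error of step-down Dunnett is 0.050 when all arms are equal, and 0.047 when M equals P+M and P is shifted by 1 SD.

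**Step 6: Holm over two.** Power for P+M v M at 0.7/1.0 SD is 75.8%, against 75.9% for step-down Dunnett. If only one effect is real, Holm rests mainly on its first step, 2.281 instead of 2.249. At d = 0.7 that means about 66.7% instead of 67.8%.

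**The case against.** ANOVA with Tukey is valid. It controls the family error, answers both comparisons in the aim, and biases nothing. Readers of a trial with two single-technique arms may also want a test of P v M. This stands, and it makes the point an improvement in efficiency rather than the correction of an error.

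Three stronger readings are tempting, and none is supported.

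- **That every post hoc method in the plan corrects for three pairs.** Only Tukey does so by construction. No adjustment is stated for Dunn and no divisor for Bonferroni. If Bonferroni were taken over three pairs, the cost against two would be at most 6.3 points on a t-test scale, but the text does not fix this.
- **That testing P v M costs the full 13 points in the 0.7/1.0 SD case.** That comparison changes both the family and the move to stepwise testing. The closed all-pairs test keeps P v M and reaches the same 75.9%. It trails step-down Dunnett by about 2 points at 0.6/0.6 SD and by about 1 at 0.8/0.8, and leads by about 3 when the P+M v P difference is zero.
- **That the change is worth 12% more patients.** That ratio describes interval width under single-step Dunnett, and the step-down test does not come with those simple intervals. At 80% power for one contrast, the single-step figure is about 9%.

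It is also fair to object that the power figures apply only to outcomes analysed as means. If an outcome fails the normality check, Dunn applies and these figures do not describe it. Dropping the omnibus test adds little in itself, at most about 1.5 points in the scenarios tried.

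**Conclusion.** The point holds as a cheap gain in efficiency. The aim asks for two contrasts, and the method for means pays for three. Like for like, the third pair costs at most about 5 points of power per contrast. Moving from Tukey to a stepwise test of the two contrasts gains about 5 to 13 points for P+M v M at assumed differences of 0.6 to 0.8 SD. The gain is near 5 when only one effect is real, and no more than 4 for a contrast with a true difference of 1.0 SD, where power is already high.

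These sizes rest on two-sided 0.05, 30 analysed per arm, normal outcomes with equal SDs, and effect sizes the documents do not supply. No planned power exists to compare them with. For ranks and rates, what is established is that the family is unstated, not that power is lost.

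**What to change.** In the Statistical Analysis section, before any unblinded data are seen:

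1. Name P+M v P and P+M v M as the confirmatory family.
2. For means, test the two contrasts by step-down Dunnett with P+M as the common arm and no ANOVA gate. Holm over the two is an alternative with almost the same power that needs only ordinary p-values.
3. For ranks and proportions, use Holm over the same two contrasts, and state this in place of the open Dunn and Bonferroni wording.
4. Report P v M descriptively, with an interval.

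The cost is wording only: no extra patients, procedures or data. The downside is that P v M loses its confirmatory test. If that test is wanted, use the closed procedure for means instead: the omnibus F at 0.05, then each pair at 0.05. It controls the family error for exactly three groups and keeps nearly the same power for the two contrasts in the aim.
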